7.3.4 Viral Safety Tests

Viral marker samples will be taken at screening, before the first NewGam infusion at Visit 2 and at the termination visit. Viral safety will be determined by serology tests for HIV, HBV and HCV at the central laboratory.

A screening and termination visit retention sample will be collected and stored frozen at $\leq -70^{\circ}\text{C}$ at the central laboratory for possible future testing.

7.3.5 Vital Signs and Physical Examination

To evaluate short-term tolerance, close monitoring of vital signs including pulse and respiratory rate, blood pressure and body temperature will be performed at time points specified in Section 6.1. Measurements will be carried out before the start of each infusion, at least once during each infusion, and up to 1 hour after end of infusion. Hemodynamic changes may occur during IGIV infusion and minor changes in pulse and blood pressure are frequent. For this reason, only changes in vital signs considered clinically significant by the Investigator are to be reported as AEs. In case fever occurs, temperature will be measured every morning until the body temperature is normalized. Fever will be defined as a body temperature >37.8 °C orally, >38.2 °C rectally, >38 °C axillary, >38.2 °C tympanic, and has to be documented as an AE.

Weight will be recorded at each infusion visit and reported to the pharmacist or designee as it is needed for the preparation of the next study medication dosage by the unblinded pharmacist or designee 3 weeks later. Height will be measured at baseline.

7.3.6 Other Relevant Safety Information

Post study related safety reports:

Any SAE which occurs up to four weeks after the last IMP administration should be reported by the Investigator to the Sponsor if the Investigator becomes aware of it. Proactive monitoring for post study SAEs is not required.

If a post study SAE is identified, the Investigator should complete an SAE form. Relation to the clinical study should be stated on the report.

If a patient dies within 4 weeks after the last IMP administration, this should be reported as well, regardless of being considered treatment-related or not.

Pregnancies:

Every effort will be made to avoid a pregnancy during the use of an IMP. WOCBP using an acceptable effective contraceptive method during the study will be enrolled.

WOCBP is defined as fertile woman, following menarche and until becoming post-menopausal unless permanently sterile. Permanent sterilisation methods include hysterectomy, bilateral salpingectomy and bilateral oophorectomy. A postmenopausal state is defined as no menses for 12 months without an alternative medical cause.

Acceptable effective contraceptive measures include the following:

- combined (estrogen and progestogen containing) hormonal contraception associated with inhibition of ovulation (oral, intravaginal, transdermal)
- progestogen-only hormonal contraception associated with inhibition of ovulation (oral, injectable, implantable)
- progestogen-only oral hormonal contraception, where inhibition of ovulation is not the primary mode of action
- intrauterine device
- intrauterine hormone-releasing system
- bilateral tubal occlusion
- vasectomised partner

- sexual abstinence
- male or female condom with or without spermicide
- cap, diaphragm or sponge with spermicide

Pregnancies occurring during the study (fetal exposure to the IMP) need to be reported.

In case of pregnancy during the study the Investigator is asked to complete the pregnancy notification form and to send it (by fax) to the CPM or designee.

Follow-up information on the outcome of both mother and fetus will be requested by a Sponsor representative.

Overdose, interaction, misuse, medication error and lack of efficacy:

The following safety relevant information should be reported as an AE or, if the reaction fulfils one of the criteria for seriousness, as a SAE.

Drug overdose:

An overdose is a deliberate or inadvertent administration of a treatment at a dose higher than that specified in the protocol, and higher than the known therapeutic dose and of clinical relevance. The reaction must be clearly identified as an overdose.

Interaction:

A drug interaction is a situation in which a substance/medicinal product affects the activity of an IMP, i.e., the effects are increased or decreased, or they produce an effect that none of the products exhibits on its own. The reaction must be clearly identified as drug interaction.

Misuse:

Misuse is the deliberate administration or use of the medicinal product outside its described indication or outside the current state of the art medical practice (off-label-use). The reaction must be clearly identified as misuse.

Medication error:

Medication error involves the inadvertent administration or unintended use of a medicinal product which may be caused by the naming, presentation of pharmaceutical form/packaging, instructions for use/labelling. The reaction must be clearly identified as a medication error.

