The hospital pharmacist or designee will send the 3 infusion bags per patient (potentially already fixed to the opaque infusion line) to the ward on the corresponding days. At the ward, the infusions will be given according to the order stated on the label (“1 of 3”, “2 of 3”, on Day 1 and “3 of 3” on Day 2). To further assure the double-blind character of this study, the physician or designee who applies the medication to the patient will not be involved in any other evaluations other than drawing blood samples or checking for vital signs, i.e. will not be involved in any patient ratings (e.g. INCAT, I-RODS, NCS, grip strength). In parallel, all Investigators for the electrophysiological or neurological evaluations will not be involved in the application of the medication.

Blinding of the patient: The patient will be blinded to the medication throughout the entire study. Because of the opaque (non-transparent) infusion line and overpouches, the patient will not be able to see the medication he/she is treated with.

Therefore, patients deteriorating (increase in adjusted INCAT disability score of at least 1 point) in the 0.5 and 1.0 g/kg NewGam arms after Week 3 and before Week 18 or remaining stable (unchanged adjusted INCAT disability score from baseline) by Week 6, and thus receiving 2 additional treatments with 2.0 g/kg NewGam, will continue with all study procedures as described in this protocol and will remain blinded as no serious safety issues are expected related to these procedures for patients continuing with NewGam treatment, while patients on 2.0 g/kg NewGam will drop-out if they deteriorate or are stable at Week 6.

The local study file will contain code break envelopes (or detailed instructions for the electronic equivalent thereof). If paper envelopes are used, the monitor will check the envelopes at each visit. Any breaking of the blind has to be documented with date, time, person, and reason.

The Investigator has to notify the Sponsor as soon as possible about the unblinding of a patient.

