7.3 Safety Assessments

Any of the following drug safety information shall be collected:

Adverse events (AEs) and serious adverse events (SAEs) temporally associated with administration of IMP or saline solution (definitions and reporting requirements see Sections 7.3.1 and 7.3.2)

Pregnancies, drug overdose, interaction, medication error, lack of efficacy, post-study SAEs (see Section 7.3.6)

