7.3.1.2 Collection

The condition of the patient will be monitored throughout the study. At each visit, whether scheduled or unscheduled, AEs will be elicited using a standard non-leading question such as “How have you been since the last visit / during the previous study period?” In addition, the patient diaries (if applicable) will be checked by the Investigator for any documented event.

Any AE or ADR which occurs during the study will be noted in detail on the appropriate pages of the eCRF. If the patient reports several signs or symptoms, which represent a single

syndrome or diagnosis, the latter should be recorded in the eCRF. The Investigator responsible will grade the severity of all AEs or ADRs (mild, moderate or severe), the seriousness (non-serious or serious) and causality, as defined below (Sections 7.3.1.3, 7.3.1.4 and 7.3.2). The Sponsor is responsible to assess the expectedness of each ADR (expected or unexpected), as defined below (Section 7.3.1.4).

In the event of clinically significant abnormal laboratory findings, the tests will be repeated and followed-up until they have returned to normal and/or an adequate explanation is available.

Diseases, signs and symptoms and/or laboratory abnormalities already existing before the first administration of IMP are not considered as AEs when observed at a later stage unless they represent an exacerbation in intensity or frequency (worsening).

The Investigator responsible should always provide detailed information concerning any abnormalities and the nature of, and reasons for any necessary action(s), as well as any other observations or comments, which are useful for the interpretation and understanding of the patients' AEs or ADRs.

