11.1. Adverse Events

All reported AEs will be coded according to MedDRA.

An Adverse Event (AE) is defined as treatment-emergent, if first onset or worsening is after start of the first infusion of *NewGam*. Only treatment-emergent AEs (TEAE) are accounted for in the analysis.

A TEAE will be considered to be temporally associated with the infusion (or 'infusional') if it starts during or within 72 hours of the end of the infusion.

All treatment-emergent AEs for each patient, including multiple occurrences of the same event, will be listed in full detail, including reported term, MedDRA preferred term and system organ class, onset, duration, time to the AE occurrence from last dose, causality, dosage, severity, seriousness and actions taken.

For each dose group and for the study as a whole the following will be given:

- Total number of TEAEs reported
- Number of temporally associated TEAEs
- Number and percentage of infusions temporally associated with one or more TEAE
- Number of temporally associated TEAEs divided by the total number of infusions

On a per patient basis the incidence of TEAEs will be summarized by system organ class, preferred term and maximum severity. If a patient experiences an adverse event more than once the event at the most severe occurrence will be considered. Patients will be included only once under each system organ class and only once in the overall totals under the most severe event occurrence.

TEAEs will be summarized by strongest relationship to study medication by system organ class and preferred term. If a patient experiences an adverse event more than once the event most related to study medication will be considered. Patients will be included only once under each system organ class and only once in the overall totals under the most related to study medication occurrence.

Incidences of TEAEs (given as the number and percentage of patients) will be summarized overall and for each dose group as follows:

- Any TEAE
- Any serious TEAE
- Any TEAE probably or possibly related to the trial drug
- Any severe TEAE
- Any withdrawal due to TEAE
- Any significant TEAE
- Any TEAE by MedDRA System Organ Class (SOC) and MedDRA Preferred Term (PT)

Significant AEs fulfill at least one of the following criteria:

- any concomitant medication or therapy started due to the AE
- Study treatment was stopped/withdrawn or dose changed

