11.5. Physical Examination

A general physical examination will be performed at the screening visit, and relevant findings will be documented; the physical examination will be repeated at visits 2, 6, and at the end of study.

Changes in results of physical examination will be summarized by body system and visit. Any clinically relevant worsening from the baseline status will be documented as an AE.

12. Reporting Conventions

The following reporting conventions will be adopted for the presentation of study data. These conventions will enhance the review process and help to standardize presentation with common notations.

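### CIDP worsening can be recorded as an adverse event and SAP 11.1 does not separate it, so dose comparisons of TEAE rows can mix efficacy failure with harm

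*Protocol*

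**What the plan says.** **Lack of efficacy.** Protocol 7.3 lists it among the safety information to be collected, on a line separate from AEs and SAEs, and refers to 7.3.6. There it appears in the sub-heading "Overdose, interaction, misuse, medication error and lack of efficacy", followed by the rule "The following safety relevant information should be reported as an AE or, if the reaction fulfils one of the criteria for seriousness, as a SAE". The text below defines overdose, interaction, misuse and medication error. It has no entry for lack of efficacy.

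**Worsening.** Protocol 7.3.1.2 does not count conditions that existed before the first IMP administration as AEs, "unless they represent an exacerbation in intensity or frequency (worsening". SAP 11.5, on the physical examination, says: "Any clinically relevant worsening from the baseline status will be documented as an AE".

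**Tabulation.** SAP 11.1 summarises all TEAEs by dose group, with a row for "Any withdrawal due to TEAE" and one for significant TEAEs. A significant AE includes one after which study treatment was stopped or the dose changed. Protocol 7.3.1.1 defines withdrawal due to an AE as an AE that leads to IMP being discontinued. Neither document says how CIDP worsening or lack of efficacy is handled in these tables.

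**Consequence of failure by arm.** Protocol 5.8 says "patients on 2.0 g/kg NewGam will drop-out if they deteriorate or are stable at Week 6". In the 0.5 and 1.0 g/kg arms, patients who deteriorate after Week 3 and before Week 18, or are stable at Week 6, receive two 2.0 g/kg rescue infusions (Protocol 3.3.1, 5.7, 6.1.4).

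**The concern.** Comparing safety across the three doses is part of a secondary objective (Protocol 2.2). If worsening of the disease under treatment enters the TEAE counts, the any-TEAE row mixes two quantities that may run in opposite directions with dose: harm from IGIV and failure of IGIV. The withdrawal row has a further problem. The trigger is the same in all arms but the consequence is not, so the row could differ between doses because of the exit rule and not because of tolerability. A reader of the CSR could then take an excess of TEAE withdrawals at 2.0 g/kg as poorer tolerability.

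**Working it through.** The documents give no figure on this point, so the check is to follow one event through the rules and then to set out the scale.

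**1. One event, three arms.** Take a patient whose adjusted INCAT score rises by at least 1 point over Week 0 (worsening in SAP 8.4) after Week 3 and before Week 18, and whose site records this as an AE.

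| Step | 2.0 g/kg | 0.5 or 1.0 g/kg |
|---|---|---|
| AE by worsening (Protocol 7.3.1.2) | can qualify | can qualify |
| Next step (Protocol 3.3.1, 5.5, 5.7) | drops out, end-of-study visit | two rescue infusions, then end-of-study visit |
| Withdrawal due to AE (Protocol 7.3.1.1) | can qualify | does not follow from the trigger |
| Significant AE (SAP 11.1) | can qualify: treatment stopped | can qualify: dose changed |

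Protocol 7.3.1.6 includes a dose increase among the recorded actions on IMP, so the dose-change route is open in practice. Detection also differs. In the Week 6 to Week 9 scenario of Protocol 5.5, a 2.0 g/kg patient has the end-of-study visit, with its physical/neurological examination, at Week 9. A rescued patient has no scheduled examination until Week 12, after a rescue dose.

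**2. Where the chain is weaker.**
- Stable at Week 6 means an unchanged score. Nothing has worsened, so Protocol 7.3.1.2 and SAP 11.5 do not apply. Only the undefined item in 7.3.6 could make this an AE.
- Protocol 5.7 has patients who deteriorate after Week 18 drop out, without limiting this to 2.0 g/kg. The other arms can therefore contribute to the withdrawal row too.

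**3. Scale of the withdrawal row.** 140 patients at 1:2:1 give 140/4 = 35, 140/2 = 70 and 35. One coded exit adds 1/35 = 2.9 points at 2.0 g/kg; one at 1.0 g/kg adds 1/70 = 1.4 points. The share e of 2.0 g/kg patients who exit this way is not in the documents. Assume a range for e, every exit coded as an AE, and a rate r of other AE withdrawals that is independent of the exits. The row then shows r + (1 − r)e:

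| e (assumed) | patients, 35e | row if r = 0% | row if r = 5% |
|---|---|---|---|
| 10% | 3.5 | 10% | 14.5% |
| 20% | 7 | 20% | 24% |
| 30% | 10.5 | 30% | 33.5% |
| 40% | 14 | 40% | 43% |

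These are upper bounds for each e. If no exit is coded as an AE, the contribution is zero.

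**4. Any-TEAE row.** Let a be the rate of other TEAEs, b the rate of efficacy failure and c the share of failures coded as AEs. With independence, the observed rate is 1 − (1 − a)(1 − cb). Assume a = 40/50/60% for 0.5/1.0/2.0 g/kg.
- b = 60/40/30%, c = 1: 1 − 0.6×0.4 = 76%, 1 − 0.5×0.6 = 70%, 1 − 0.4×0.7 = 72%. The gradient is lost.
- Same b, c = 1/4: 1 − 0.6×0.85 = 49%, 1 − 0.5×0.90 = 55%, 1 − 0.4×0.925 = 63%. The gradient survives.
- b = 40% in every arm, c = 1: 1 − 0.6×0.6 = 64%, 1 − 0.5×0.6 = 70%, 1 − 0.4×0.6 = 76%. The gradient survives, compressed from 20 to 12 points.

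Masking is possible, but it depends on rates and coding that the documents do not give.

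**The case against.** The strongest reply is that no text calls these exits AE withdrawals. The protocol calls them drop-outs, Protocol 4.4.1 gives ineffective therapy as an example under withdrawal of consent, and an AE withdrawal needs both a recorded AE and a causal link to stopping IMP. Lack of efficacy has no definition or trigger in 7.3.6, and Protocol 9.2.3.6 has additional safety information listed and reviewed. Other displays also help: withdrawals by reason (SAP 9.1), deteriorations by dose group and effect on disposition (SAP 10.2), and TEAEs by system organ class and preferred term, relatedness, seriousness and severity (SAP 11.1). Rescue also brings treatment to an early end in most scenarios of Protocol 5.5, so part of the contrast between arms is timing. The safety analysis is descriptive, so no test is biased.

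Much of this stands, and it rules out saying that such exits will be counted as TEAE withdrawals. It does not close the gap. The worsening rule in Protocol 7.3.1.2 does not depend on 7.3.6 and fits a rise in INCAT score. The other displays sit beside the any-TEAE, withdrawal and significant-TEAE rows without removing anything from them.

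Taking the events out of the main tables would go too far. Protocol 9.2.3.1 commits to reporting all TEAEs, and removal could hide genuine worsening.

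**Conclusion.** The concern holds in a limited form. For deteriorating patients, the rules as written allow CIDP worsening to be recorded as an AE, and SAP 11.1 gives no means of separating it. Through the different exit rules, the same event can reach the withdrawal row mainly at 2.0 g/kg. Dose comparisons of the any-TEAE, withdrawal and significant-TEAE rows can therefore mix efficacy failure with harm. The size cannot be stated: 2.9 points per coded exit at 2.0 g/kg, and zero if sites code none.

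A reader might infer more: that every 2.0 g/kg exit is a TEAE withdrawal, up to 14 of 35 against about none elsewhere, or that the dose gradient in harm must disappear. The documents do not support either. The 14 of 35 needs an assumed 40% exit share and full AE coding. Patients stable at Week 6 are affected only if a site reports lack of efficacy as an AE. Exits after Week 18 are not confined to one arm. The loss of gradient appears in only one of the three assumed cases above.

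**What to change.** In SAP 11.1, before unblinding:
- Flag at blinded data review the AEs that record lack of efficacy or CIDP worsening, using an agreed preferred-term list plus the INCAT worsening criterion of SAP 8.4. The flag should not use the action taken, because exit versus rescue points to the arm.
- Keep the all-TEAE tables as the main display. Add any-TEAE, TEAE-withdrawal and significant-TEAE rows by dose group that exclude the flagged events.
- Tabulate the flagged events separately by dose group.

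In SAP 9.1, give protocol-mandated exits their own disposition reason.

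SAE reporting and the exit and rescue rules stay as they are. The cost is some SAP wording, one flag at data review and a few extra tables.

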8 DATA HANDLING AND RECORD KEEPING

8.1 Documentation of Data

8.1.1 Source Data and Records

Source data are defined as all the information related to clinical findings, observations, or other activities in the study, written down in original records or certified copies of original records allowing reconstruction and evaluation of the clinical study.

The Investigator will maintain adequate source records (e.g., case histories or patient files for each patient enrolled). Source records should be preserved for the maximum period of time required by local regulations.

For each patient enrolled, the Investigator will indicate in the source records that the patient participates in this study.

All data entered into the eCRF must be supported by source data in the patient records with the exceptions listed in Section 8.1.2.

The Investigator will permit study-related monitoring, audit(s), IEC/IRB review(s) and regulatory inspection(s), by providing direct access to source data/records.

The Investigator may authorize site staff (e.g., sub-Investigators, nurses) to enter study data into the eCRF. This must be documented in the „Delegation of Authority Log“, signed by the Investigator.

8.1.2 Electronic Case Report Forms

For each patient enrolled, an electronic CRF (eCRF) will be completed within the Electronic Data Capture (EDC) system and approved by the Investigator or an authorized sub-Investigator.

Study site staff (e.g. research nurse) will be responsible for entering patient data into the validated EDC system. All site personnel will be trained on the EDC system and study specific eCRFs prior to receiving access to the live database for data entry. The site is also provided with the approved eCRF Completion Guidelines which will assist in data entry and data issues/questions. The site will be notified once the database is active to begin data entry. Additional site training may be provided as refreshers throughout the study, if needed. All persons allowed to enter or change eCRF data must appear on the delegation of authority log.

8.1.3 Changes to Case Report Form Data

Monitors will perform source data verification (SDV) as defined for the study.

If any errors or discrepancies in the eCRFs are found during data entry or review, discrepancies will be generated programmatically within the EDC system, and ‘manual’ queries will be generated by either a monitor or Data Management.

Discrepancies and queries can only be corrected by the Investigator(s) or other authorized site personnel. An audit trail documents all changes to the data over the entire study period. If the reason for a change is not obvious, a comment must be supplied within the query’s response, stating the reason for the change, prior to closing. The study monitor should provide guidance to Investigator(s) and the Investigator(s)’ designated representatives on making such corrections.

Once queries have been resolved by the site staff, the resolutions are assessed by Data Management. If the query response provided confirms the data as correct, the discrepancy will be closed. If the response does not adequately address the question raised, a new query will be issued for further clarification.

Manual checks are performed and programs are run throughout the study until the data is clean and the database is ready for lock. All discrepancies will be resolved prior to database lock. There will be a final run of the programmed checks to ensure all discrepancies are closed out, SDV will be confirmed as complete by the monitor, and all eCRFs will be approved by the Investigator prior to database lock.

